# CONFIDENTIAL

ΙΤΤ	intention to treat: The principle that asserts that the effect of a treatment policy can be best assessed by evaluating on the basis of the intention to treat a participant (that is, the planned treatment regimen) rather than the actual treatment given. It has the consequence that participant allocated to a treatment group should be followed up, assessed, and analyzed as members of that group irrespective of their compliance to the planned course of treatment.	
IWRS	interactive web-response system	
JAK	Janus kinase	
LDH	lactate dehydrogenase	
MDRD	Modification of Diet in Renal Disease	
MERS	Middle East respiratory syndrome	
NAKs	numb-associated kinases	
NEWS	National Early Warning Score	
NIAID	National Institute of Allergy and Infectious Diseases	
NIAID-OS	NIAID ordinal scale	
NIH	National Institutes of Health	
NOAEL	no-observed-adverse-effect level	
NONMEM	nonlinear mixed effects modeling	
NP	nasopharyngeal	
NRI	non-responder imputation	
NSAID	nonsteroidal anti-inflammatory drug	
OS	ordinal scale	
ΡΑ	posterior-anterior	
participant	Equivalent to Clinical Data Interchange Standards Consortium (CDISC) term "subject," meaning an individual who participates in a clinical trial, either as recipient of an investigational medicinal product or as a control.	
	In this protocol, the term "participant" is used to indicate an individual who participates in a clinical trial, either as a recipient of an investigational medicinal product or as a control. This usage reflects preferences indicated by patient advocates to more accurately reflect the role of people who take part in clinical trials. The term "patient" is also used to indicate an individual who participates in this clinical trial.	
PD	pharmacodynamics	
PE	pulmonary embolism	
РК	pharmacokinetics	
PK	pharmacokinetics	
QD	once daily	
RA	rheumatoid arthritis	

RNA	ribonucleic acid	
SAE	serious adverse event	
SAP	statistical analysis plan	
SARS	severe acute respiratory syndrome	
SARS-CoV-2	novel SARS coronavirus 2	
screen	The act of determining if an individual meets minimum requirements to become part of a pool of potential candidates for participation in a clinical study.	
SI	international system of units	
SoA	Schedule of Activities	
study drug	See "study intervention"	
study intervention	Any investigational intervention, marketed product, placebo, or medical device intended to be administered to a study participant according to the study protocol	
ТВ	tuberculosis	
TBL	total bilirubin level	
TEAE	Treatment-emergent adverse event: An untoward medical occurrence that emerges during a defined treatment period, having been absent pretreatment, or worsens relative to the pretreatment state, and does not necessarily have to have a causal relationship with this treatment.	
TNFi	tumor necrosis factor inhibitor	
ULN	upper limit of normal	
VTE	venous thromboembolism	
WBC	white blood cell	
WHO	World Health Organization	
WOCBP	women of childbearing potential	

# **10.6.** Appendix 6: Protocol Amendment History

The Protocol Amendment Summary of Changes Table for the current amendment is located directly before the Table of Contents (TOC).

#### Amendment D (20 October 2020):

This amendment is considered to be substantial based on the criteria set forth in Article 10(a) of Directive 2001/20/EC of the European Parliament and the Council of the European Union.

#### **Overall Rationale for the Amendment:**

The main purpose of this protocol amendment is to modify the study inclusion criteria and provide the opportunity for the sample size to be increased (sample size re-estimation) during an interim analysis. These changes are based on newly available data from the ACTT-2 study and on evolution in clinical management of the disease. In addition, based on regulatory feedback, a follow-up visit is added at Day 60.

Sections # and Name	Description of Change	Brief Rationale
1.1, Synopsis: Overall Design	Added a Day 60 assessment in the	To evaluate safety and efficacy at
	follow-up period and increased the	Day 60 for this patient population
	total maximum duration.	based on regulatory feedback.
1.1, Synopsis: Number of	Changed sample size to 1000	To increase sample size based on
Participants	patients. Added text for a sample size	ACTT-2 data and modeling
	re-estimation to potentially increase	assessments. Included a sample size
	the final sample size beyond 1000	re-estimation to maintain an
	patients.	adequately powered study.
1.2, Schema	Changed figure to include a Day 60	To add a Day 60 assessment based
	assessment.	on regulatory feedback.
1.3, Schedule of Activities	Added a column for Day 60	To add a Day 60 assessment based
	assessments.	on regulatory feedback.
	Added text clarifying the conduct of	To provide clarity on study visit
	various procedures.	procedures.
	Added visit windows for patients	To provide greater visit window
	discharged from hospital.	flexibility for patients who have
		been discharged from the hospital.
2.2, Background	Added citations for NIH and WHO	To reflect current NIH and WHO
	guidelines on use of corticosteroids.	guidelines.
3, Objectives and Endpoints	Added an exploratory objective for	To reflect addition of Day 60
	long-term (at least Day 60) clinical	assessment based on regulatory
	outcomes.	feedback.
4.1, Overall Design	Added a Day 60 assessment in the	Regulatory feedback, as stated for
	follow-up period and increased the	Section 1.1; see also rationale for
	total maximum duration; changed	Section 5.1.
	description of study population.	
4.2, Scientific Rationale for	Added a statement and a phrase about	Regulatory feedback, as stated for
Study Design	the Day 60 assessment.	Section 1.1

Sections # and Name	Description of Change	Brief Rationale
4.3, Justification for Dose	Added bold font format and	To clarify for investigators; these
	clarifying text about patients who	patients will remain on blinded 2-mg
	have eGFR $\geq$ 30 mL/min/1.73 m  to	dose (baricitinib or placebo) during
	<60 mL/min/1.73 m  at screening.	treatment.
5.1, Inclusion Criteria	Revised protocol inclusion criterion	Changed study population based on
	#4, stating that patients must require	ACTT-2 data availability and
	oxygen supplementation at entry and	population that derived greatest
	randomization.	benefit in recovery and mortality.
6.1, Study Interventions	Added bold font format and	To clarify for investigators; these
Administered	clarifying text about patients who	patients will remain on blinded 2-mg
	have eGFR $\geq$ 30 mL/min/1.73 m  to	dose (baricitinib or placebo) during
	$<60 \text{ mL/min}/1.73 \text{ m}^2$ at screening.	treatment.
		To clarify for investigators: Patients
	Added clarifying text about	who are discharged from hospital
	investigational product after patient's	will not be given investigational
	discharge from hospital.	product for home use.
6.5.3, Prohibited Concomitant	Added a clarification in a	Baricitinib for treatment of
Therapy	parenthetical phrase about prohibited	COVID-19 is required for certain
	concomitant medication.	participants according to the study
		design. However, JAK inhibitors are
		prohibited as concomitant therapy
		during the study.
6.6, Dose Modification	Added words "equal to or"; corrected	To provide consistency between text
	some symbols, replacing $>$ with $\ge$ .	statement and the "greater than or
		equal to" symbol $(\geq)$ in the
		preceding sentences.
7.1.1, Criteria for Permanent	Added a phrase about the Day 60	Regulatory feedback, as stated for
Discontinuation of Study	assessment.	Section 1.1
Drug		
8.1.1, COVID-19 Clinical Status	Added a statement about a Day 60	Regulatory feedback, as stated for
Assessment	assessment.	Section 1.1
8.3.1, Time Period and	Added a statement that serious	To clarify the SAE reporting process
Frequency for Collecting	adverse events, including death,	and to align with language already in
AEs and SAEs	caused by COVID-19 disease	Section 10.3.
	progression should not be reported	
	on the SAE form unless the	
	investigator deems them to be	
	possibly related to study treatment.	
9.2, Sample Size Determination	Moved the assumptions of the sample	To update the assumptions used to
	size as stated in amendment C, and	calculate the new sample size. The
	provided new assumptions for	assumptions use modeling inclusive
	amendment D.	of data available from the ACTT-2
		study.

Sections # and Name	Description of Change	Brief Rationale
9.3, Populations for Analyses	Revised removed the phrase "within each study period" from the statement about analyzing participants according to the intervention they received.	To clarify the sentence, given that participants receive intervention in only one study period.
9.4.1, General Considerations	Added subgroups for subgroup analyses.	To assess subgroups of interest.
9.4.2, Primary Endpoint	Added statement about statistical procedure to be used to control type I error if the sample size is increased as a result of interim analysis.	To control type I error in the event of a sample size increase.
9.4.4, Safety Analyses	Removed text about the analysis period being defined as the treatment period plus up to 30 days off-drug follow-up time. Removed text stating that the	To reflect that safety assessments will include safety data collected within the Treatment period. To provide clarity.
	treatment period will be used as the postbaseline period for the analysis. Removed text about summary of treatment-related TEAEs.	To remove a nonstandard summary.
9.5, Interim Analyses	Added sample size re-estimation considerations of interim analyses. Added that unblinding details may be specified in DMC charter or in SAP or separate unblinding plan document.	To reflect that sample size re-estimation may be a rationale for interim analyses. To provide a more comprehensive list of documents where unblinding details may be described.
9.6, Data Monitoring Committee	Added a phrase about sample size	To maintain an adequately powered
(DMC)	re-estimation.	study; see rationale for Section 1.1.
10.2.1, Clinical Laboratory Tests	Added a note that cell morphology is performed "if applicable and/or needed."	To clarify conduct of assessment if warranted.
10.3.1, Events Not Meeting AE Definition	Added clarifying text, stating that disease being studied or expected progression is not reported unless more severe than expected "or results in death".	To clarify reporting of adverse events given death is endpoint being measured.
10.3.2, Definition of SAE	Clarified definition of SAE if death is due to progression of COVID-19 disease.	To clarify that SAE due to progression of COVID-19 disease is reported as adverse event.
11, References	Added references and links for updated guidance documents from NIH and WHO, press release for the ACTT-2 study, Gao et al., Cui et al., and Brannath et al.	To support statement about corticosteroid use in the protocol's background section, and to support statements about sample size in the protocol's statistical section.
various sections	Changed singular nouns to plural (for example, visit to visits ); changed verb tense from present to past.	Grammatical correctness.

# Amendment C (12 Aug 2020):

This amendment was considered to be substantial based on the criteria set forth in Article 10(a) of Directive 2001/20/EC of the European Parliament and the Council of the European Union.

#### **Overall Rationale for the Amendment:**

The main purpose of this protocol amendment was to increase the sample size to accommodate evolving changes in standard-of-care therapy, especially concomitant use of dexamethasone.

Sections # and Name	Description of Change	Brief Rationale
1.1 Synopsis: Rationale	Replaced "data on file" with citations	Information has been published,
		citations added.
1.1 Synopsis: Number of	Increased the total number of patients	Sample size was increased to
Participants and Intervention	to be randomized from the original	accommodate evolving changes in
Groups	number to a range of 600 to 1000,	standard-of-care therapy, especially
	keeping same randomization ratio	concomitant use of dexamethasone.
	and same number of treatment groups	
1.3 Schedule of Activities	Provided introductory text and	Provided clarification for situations
	clarifying text on the row called Site	in which patient is not able to have
	Visit	an on-site visit and what procedures
		should be done for telephone visit
1.3 Schedule of Activities	Updated Comments column for	Editorial change, no intended change
	physical examination row	in meaning
1.3 Schedule of Activities	Updated Comments column for chest	To clarify the acceptable timing of
	imaging row and ECG row	the procedure
1.3 Schedule of Activities	Created a separate row for Lactate	To clarify that LDH is acceptable
	dehydrogenase (LDH, which was	within 2 days of study entry
	previously written in the row for	
	clinical chemistry; updated Clinical	
	Chemistry row, removing LDH	
1.3 Schedule of Activities	Clarified text in Comments columns	To make text about lab timing
	on rows for D-dimer, ferritin,	consistent with inclusion criteria
	C-reactive protein (CRP)	requirements
1.3 Schedule of Activities	Clarified and updated text in	To clarify text per inclusion criteria
	Comments column about	requirements, if patient has
	requirements for SARS-CoV-2 viral	confirmed COVID-19 infection; also
	infection confirmation via	to provide investigator judgement for
	nasopharyngeal swab	collection of samples at other
		timepoints to reduced number of NP
		swabs, patient burden, and site
		burden
1.3 Schedule of Activities	Updated text in Comments column in	To reference a section describing
	two rows about exploratory	collection based on lab kit
	biomarker samples	availability
2.1 Study Rationale	Replaced "data on file" with	Information has been published,
	citations; updated year of United	citations added; UPSI was updated.
	States package insert (USPI)	
4.3 Justification for Dose	Replaced "data on file" with citation	Information has been published,
		citation added.

Sections # and Name	Description of Change	Brief Rationale
5.2 Exclusion Criteria	Added a note to exclusion criterion #8	To clarify corticosteroid use (dose and duration) for dexamethasone and/or other systemic corticosteroids
5.2 Exclusion Criteria	Added "or" in the phrase about deep vein thrombosis and pulmonary embolism	To clarify and support site understanding
5.2 Exclusion Criteria	Added a parenthetical reference to the aforementioned exclusion criteria following exclusion criterion #20	To support site understanding
6.1 Study Interventions Administered	Clarified dosing instructions for patients with eGFR >30 mL/min/1.73 m  to <60 mL/min/1.73 m  at screening	To support site understanding
6.3 Measures to Minimize Bias: Randomization and Blinding	Changed one of the factors for stratification: removed the symptom onset factor, and added a factor about use of dexamethasone and/or other systemic corticosteroid use at baseline for primary study condition	To accommodate evolving changes in standard-of-care therapy
6.6 Dose Modification	Clarified dosing instructions for patients with eGFR >30 mL/min/1.73 m  to <60 mL/min/1.73 m  at screening	To support site understanding
8.1.3 Other Efficacy Assessments	Clarified text on resolution of fever	To clarify the definitions and options for assessment of fever
8.2.1 Vital Signs	Revised text about body temperature, simplifying the text	To avoid redundancy and potential inconsistency. Section 8.1.3 provides the information about body temperature.
8.2.3 Electrocardiograms	Revised text about timing of ECGs that are acceptable, per the SOA	To keep text consistent with changes in the SOA, as described above
8.2.4 Chest Imaging Studies	Revised text about timing of imaging that is acceptable, per the SOA	To keep text consistent with changes in the SOA, as described above
8.8 Biomarkers	Added text about sample collection based on availability of centrally supplied lab kits	To clarify collection based on lab kit availability
9.2 Sample Size Determination	Changed the number of patients to be randomized, changed power; changed assumptions for the power calculation	To accommodate evolving changes in standard-of-care therapy
9.4.1 General Considerations	Changed text about subgroup analysis, including dexamethasone and/or other systemic corticosteroid used at baseline for primary study condition	To maintain consistency with other changes already described
9.4.1.3 Missing Data Imputation	Changed from LOCF to multiple imputation methods	To more accurately account for the variability of missing data

Sections # and Name	Description of Change	Brief Rationale
9.5 Interim Analyses	Clarified that interim analyses may	To clarify intended uses of interim
	be used for safety monitoring	analyses
9.6 Data Monitoring Committee	Added mention of external statistical	To provide clarity and to update with
	analysis; removed mention of	correct information, as no PK/PD
	population PK/PD model	modeling is planned
	development	
10.2.1 Clinical Laboratory Tests	Added text and cross-references	To provide consistency and
	about SARS-CoV-2 viral infection	flexibility of investigator assessment
	confirmation and exploratory	for collection, consistent with
	biomarker samples	inclusion criteria requirements and at other timepoints; and to clarify
		exploratory biomarker sample
		collection based on central lab kit
		availability
10.4.2 Contraception	For males and for women not of	To correct a typographical error
	childbearing potential, changed	
	verbiage from "there are no	
	conception requirements"	
	to "there are no con tra ception	
	requirements"	
10.5 Abbreviations	Defined several terms, including but	To improve ease of reading
	not limited to, ACTT, CYP, JAK,	
	NP, OS, WHO	
10.6 Protocol Amendment History	Inserted amendment B history	To maintain the history of the protocol
Section 11 References	Added Beigel, Horby, Stebbing	Information has been published,
	publications; updated date of the	citations added, USPI updated.
	USPI; updated access date of	_
	Summary of Product Characteristics	
various sections	Added punctuation marks that were	Editorial consistency
	previously missing	

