# 4.2. Scientific Rationale for Study Design

The double-blind, placebo-controlled design of this study limits potential bias in investigator assessments and enables a clearer interpretation of the effects of active drug compared to placebo (background therapy).

The primary endpoint of this study is the proportion of patients who die or require non-invasive ventilation/high-flow oxygen or invasive mechanical ventilation (including ECMO) by Day 28. Progression to requiring non-invasive or invasive mechanical ventilation is an indicator of critical disease and can occur at any timepoint after hospitalization.

Time on ventilation increases the patient's risk of complications, including pneumothorax, airway injury, alveolar damage, ventilator-associated pneumonia, and ventilator-associated tracheobronchitis, which are associated with higher death rates and longer hospital stays (Craven et al. 2009; Hess 2011; Patel 2020). An effective treatment should be able to halt progression of patients to ventilation at any time. A primary endpoint capturing progression to death or non-invasive ventilation/high-flow oxygen or invasive ventilation (including ECMO) *by* Day 28 (rather than *at* Day 28) is clinically meaningful because it utilizes all available data about the course of disease progression or resolution in response to treatment.

The addition of the subpopulation of patients requiring oxygen supplementation at baseline to the primary analysis is based on the National Institute of Allergy and Infectious Diseases (NIAID) Adaptive COVID-19 Treatment Trial 2 (ACTT-2). Patient recovery and mortality in ACTT 2 indicated treatment effect was the largest in this subset of patients. The use of dexamethasone is recommended for patients requiring oxygen supplementation or invasive mechanical ventilation per the NIH and WHO guidelines and is allowed in this study per the protocol. The impact of dexamethasone on the efficacy of baricitinib is unknown and further evaluations in the two subpopulations will provide additional results relevant to the treatment of COVID-19.

In addition, an observation of treatment effect for baricitinib to 28 days is based on US regulatory and WHO recommendations, and allows comparisons across different therapeutic agents in COVID-19 studies. Based on regulatory feedback, an additional evaluation of patients' clinical status and safety assessments will be conducted at Day 60 to evaluate safety and effectiveness for this patient population.

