Description and Derivation of Primary, Key Secondary, and Associated Supportive Analyses	Table KHAA.6.4	Added derivation details for several variables
Description of Primary, Key Secondary, and Associated Supportive Analysis	Table KHAA.6.5	Minor wording changes for clarity. Changed mLOCF to LOCF. Changed analysis for Oxygen Saturation from MI to LOCF.
Description and Derivation of Other Secondary Outcomes	Table KHAA.6.6	Added analytic details for several analyses.
Description of Other Secondary Analyses	Table KHAA.6.7	Removed analysis of time to recovery by disease duration at baseline.  Removed Fine-Gray proportional hazards regression with death as a competing risk, as death is already handled in a manner that considers it a competing risk (i.e., via IETI).
Primary Outcome and Methodology	6.11.1	Changed the final allocation of alpha for Population 1 to 99%. This change was made based on a review of blinded data that showed that Population 2 had a much smaller sample size than originally anticipated.
Key Secondary Efficacy Analyses	6.11.2	Added an analysis of all-cause mortality in the safety population.
Subgroup Analyses	6.14	Updated subgroup analyses to reflect current plans.
Interim Analyses and Data Monitoring	6.16	Removed the paragraph that suggested that a limited number of preidentified individuals may gain access to the limited unblinded data, as there is no plan to do early unblinding for PK/PD analyses.
Sample Size Re-Estimation	6.16.2	Removed the clause "(in addition to the final analysis)" as the 90% allocation of $\alpha$ to Population 1 only applied to the

Change	Section	Summary of Changes
		sample size re-estimation. For the final primary outcome analyses, 99% will be allocated to Population 1.
References	8	Added new references
Multiple Imputation	Appendix 2	Added appendix with details of the multiple imputation methodology
Exploratory Analyses	Appendix 3	Added appendix with additional exploratory analyses

Abbreviations: ANOVA = analysis of variance; DMC = Data Monitoring Committee; DOH = duration of hospitalization; IETI = infinite event time imputation; VFD = ventilator-free days.

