## 5.2. Determination of Sample Size

In protocol amendment e, the final amendment, the sample size was updated to approximately 1400 patients based on blinded review of the proportion of patients requiring oxygen supplementation without the use of dexamethasone or systemic corticosteroids at baseline and the potential that concomitant use of systemic corticosteroids may reduce the magnitude of the treatment effect.

The table below describes the power calculations for various scenarios with a total sample size of 1400. This assumes, for illustration, that  $\alpha_1$  for Population 1 is 75% of the total alpha and that 60% of the patients were taking dexamethasone or other corticosteroids at baseline.

Treatment Effect Size in Patients Who are at OS 5 or OS 6 at Baseline		Combined Effect Size	Power for at Least One of the Two Primaries to Succeed
Patients using dexamethasone or a systemic corticosteroid	Patients not using dexamethasone or a systemic corticosteroid		
0.075	0.075	0.075	81%
0.040	0.075	0.054	54%

Abbreviations: NIAID = National Institute of allergy and Infectious Diseases; OS 5 = #5 on the 8-point NIAID ordinal scale - Hospitalized, requiring supplemental oxygen; OS 6 = #6 on the 8-point NIAID ordinal scale – Hospitalized, on noninvasive ventilation or high-flow oxygen devices.

Note: Power estimates were obtained from a custom simulation program.

Amendment e also allowed for the sample size to be increased using an unblinded sample size re-estimation (Gao et al. 2008) during an interim analysis (that occurred in January 2021).

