## 6.14. Subgroup Analyses

For primary and gated secondary endpoints, following subgroup analysis will be conducted:

- baseline disease severity:
  - hospitalized not requiring supplemental oxygen, requiring ongoing medical care (OS 4)
  - hospitalized requiring supplemental oxygen by prongs or mask (OS 5)
  - hospitalized requiring noninvasive ventilation or high-flow oxygen (OS 6)
  - OS 5 and OS 6 combined
- baseline steroid use: dexamethasone and/or other systemic corticosteroid used at baseline for primary study condition (Yes/No)
- baseline remdesivir use (Yes/No)

The following subgroups categorized into disease-related characteristics and demographic characteristics will be evaluated for primary endpoint. These analyses may also be conducted selectively on key secondary endpoints if applicable:

- patient demographic and characteristics subgroups:
  - gender (male, female)
  - age group (<65, ≥65)
  - baseline weight (<60 kg, ≥60 to <100 kg, ≥100 kg)
  - baseline BMI (<25 kg/m^2, ≥25 to <30 kg/m^2, ≥30 kg/m^2)
  - race (American Indian or Alaska Native, Asian, Black or African American, Native Hawaiian or Other Pacific Islander, White, Multiple)
  - baseline renal function status: impaired (eGFR <60 mL/min/1.73 m^2) or not impaired (eGFR ≥60 mL/min/1.73 m^2)
- geographic region subgroups:
  - region (US, Europe, Rest of World)
- baseline disease-related characteristics subgroups:
  - baseline disease duration of symptoms prior to enrollment:<7 days, ≥7 days

- preexisting comorbid conditions of interest: none, any

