For subgroup analyses of categorical endpoints, a logistic regression model or proportional odds model using the Firth correction (Firth 1993) will be used to obtain a p-value for the treatment-by-subgroup interaction. The response variable will be each corresponding endpoint. The explanatory variables will be treatment, subgroup, treatment-by-subgroup interaction, and the baseline stratification variables (Section 6.1.4). Within each subgroup category, odds ratios (bariatric 4-mg over placebo) and associated CIs and p-values will be provided. Point estimates and CIs of the proportions and difference in proportions will be presented. For LOCF analyses the CIs will be based on the Newcombe-Wilson method without continuity correction. For multiple imputation analyses, proportions/percentages will be based on percentages in the multiply-imputed datasets; CIs will be based on the Wald method without continuity correction.

For ANOVA analyses of continuous endpoints, the following explanatory variables will be included for the test of interaction: treatment, subgroup, treatment-by-subgroup interaction and the baseline stratification factors (Section 6.1.4). The F test will be used to obtain a p value for treatment-by-subgroup interaction, type III sums of squares. Within each subgroup category, LS mean and associated p-values from ANOVA (using models given in Section 6.2.2) will be provided.

For the time-to-event endpoints, an unstratified log-rank test will be performed within each level of specified subgroups if sample sizes allow. Analysis of individual levels of subgroups will follow what is specified in Section 6.2.3, possibly with the use of the Firth correction.

Descriptive statistics will be provided for each treatment and stratum of a subgroup, regardless of sample size. Inferential statistics will be provided if sample sizes and event numbers are sufficiently large (e.g., >100 patients total and at least 1 event in each arm).

Additional subgroup analyses on efficacy may be performed as deemed appropriate and necessary.

Subgroup analyses for safety parameters will be specified in the List of Analyses for this study.

[Table KHAA.6.12](#) lists the analysis methods for the different subgroup analysis.

Table KHAA.6.12. Description of Subgroup Analyses for Primary and Key Secondary Endpoints

Measure	Variable	Subgroup	Analysis Method	Time Point

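### The steroid Yes/No subgroup covers OS 4 to OS 6, so its No level is not Population 2 and its interaction term also picks up differences in effect by baseline severity

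*Protocol*

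**What the plan says.** The steroid subgroup entered with Amendment C, whose log entry for Protocol 9.4.1 reads "Changed text about subgroup analysis, including dexamethasone and/or other systemic corticosteroid used at baseline for primary study condition". That entry only records the change; the current text is as follows. Protocol 9.4.1 lists steroid use at baseline for the study condition among the subgroups and plans interaction tests. SAP 6.14 carries this forward for the primary and gated secondary endpoints: "baseline steroid use: dexamethasone and/or other systemic corticosteroid used at baseline for primary study condition (Yes/No". It sets no limit by ordinal scale. Table KHAA.6.12 names Populations 1 and 2 only for the baseline severity subgroup. All other subgroups of the primary endpoint get one logistic regression line with LOCF and so fall under the general ITT rule of SAP 6.1. SAP 6.1.4 gives the severity levels as OS 4, OS 5 and OS 6.

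The interaction model is specified as follows: "The explanatory variables will be treatment, subgroup, treatment-by-subgroup interaction, and the baseline stratification variables". OS therefore enters as a main effect, with no treatment-by-OS term.

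SAP 4.1 defines Population 2 as OS 5 and 6 without steroids. The planning table (Protocol 9.2, SAP 5.2) states the steroid contrast only in that range, under the heading "Treatment Effect Size in Patients Who are at OS 5 or OS 6 at Baseline". Protocol 4.2 says of the oxygen-requiring patients: "Patient recovery and mortality in ACTT 2 indicated treatment effect was the largest in this subset of patients". It adds: "The use of dexamethasone is recommended for patients requiring oxygen supplementation or invasive mechanical ventilation per the NIH and WHO guidelines". The same section calls the impact of dexamethasone on baricitinib's efficacy unknown.

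**The concern.** OS 4 patients need no oxygen, and the guidelines that the protocol cites recommend steroids for patients who do. It is a reasonable inference that most OS 4 patients sit in the No level. If their benefit from baricitinib is smaller, as the rationale in Protocol 4.2 suggests, they pull the No estimate down for a reason unrelated to steroids. Adjusting for OS as a main effect corrects for baseline risk. It does not let the treatment effect differ by OS.

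The plan analyses Population 2 on its own but lists no matching estimate for OS 5/6 patients on steroids and no test of one against the other. That is the contrast used in the planning table, and it bears directly on the question Protocol 4.2 leaves open. The imputation strata in SAP 6.4.3 already separate these groups; the subgroup analysis merges them again. The steroid-by-remdesivir groups in Appendix 3 have the same gap.

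Two facts affect the size. Oxygen is now required at entry (Protocol 5.1, criterion 4), so OS 4 patients should come mainly from earlier enrolment. SAP 3 also reports that "Population 2 had a much smaller sample size than originally anticipated", which raises the weight of OS 4 within the No level.

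**Working it through.** **Inputs from the documents.** N = 1400, 1:1; effect 0.075 without and 0.040 with steroids in OS 5/6; 60% on steroids for planning (Protocol 9.2, SAP 5.2).

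**Plan's own figure.** 0.6 × 0.040 + 0.4 × 0.075 = 0.054, as stated.

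**Assumptions not in the documents.** OS 4 share s = 5-20%; Population 2 share of OS 5/6, p = 15-40%; no steroid use in OS 4; placebo risk 27% in OS 5/6 and 14% in OS 4; OS 4 effect 0 or 2 points.

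**Target contrast in OS 5/6.**
- No: (0.195/0.805)/(0.27/0.73) = 0.655
- Yes: (0.23/0.77)/(0.27/0.73) = 0.808
- Ratio No/Yes = 0.655/0.808 = 0.81. The risk-difference contrast is 7.5 − 4.0 = 3.5 points.

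**Planned analysis.** The OS 4 fraction of the No level is w = s/[s + (1 − s)p]. With no OS 4 effect, the crude No risk difference is 7.5(1 − w), against 4.0 for Yes. The ratio comes from fitting the SAP 6.14 terms (treatment, steroid, their interaction, OS main effect) to expected cell counts. Age, region and the Firth correction are left out.

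| s, p | w | Crude No, points | Crude No − Yes | Ratio No/Yes |
|---|---|---|---|---|
| 5%, 40% | 0.05/0.43 = 0.116 | 6.63 | +2.63 | 0.84 |
| 10%, 15% | 0.10/0.235 = 0.426 | 4.31 | +0.31 | 0.94 |
| 15%, 15% | 0.15/0.2775 = 0.541 | 3.45 | −0.55 | 0.98 |
| 20%, 15% | 0.20/0.32 = 0.625 | 2.81 | −1.19 | 1.02 |

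With a 2-point effect in OS 4, the crude contrast 7.5(1 − w) + 2w − 4.0 runs from +2.9 to +0.1, and the ratio from about 0.83 to 0.92.

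**No true steroid interaction.** Take 0.075 in both OS 5/6 groups, none in OS 4, s = 15%, p = 20%. Then w = 0.15/0.32 = 0.469 and crude No is 7.5 × 0.531 = 3.98, against 7.5 for Yes. The fitted ratio is about 1.17 instead of 1.00.

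**No distortion.** If OS 4 has the same odds ratio as Population 2, the fitted ratio stays at the OS 5/6 value.

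**Power of the interaction test (two-sided 5%).** In the four table scenarios it is 5-10% as planned and 8-12% within OS 5/6. With all 1400 patients at OS 5/6, 40% not on steroids and 25% placebo risk, it is 13.6%. At p = 15% and s = 15%, the 95% interval for the ratio within OS 5/6 is about 0.38 to 1.73.

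**The case against.** The best defence is that little depends on this test. It is outside the multiplicity scheme of SAP 6.6. Population 2 has its own primary analysis without OS 4. OS 4, OS 5, OS 6 and OS 5/6 combined are reported as subgroups, so a different OS 4 effect would be visible. SAP 6.14 also leaves room for further subgroup analyses. The OS 4 share, steroid use and event rate are not given, and Protocol 4.2 says only that the effect was largest in the oxygen-requiring subset, not that it was absent at OS 4. Low power is the larger reason a real interaction would be missed, before or after any change.

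All of that stands, and it limits the weight of the point. It does not supply the missing contrast: none of those analyses estimates OS 5/6 patients on steroids or compares them with Population 2. With a weak test, readers will rely on the two subgroup estimates, and the No estimate is the one affected.

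A reader might infer more, namely that the planned test would hide or reverse a real steroid effect. The negative crude contrasts above invite that reading, but they are not the tested quantity. On the odds-ratio scale the ratio passes 1 in only one of the four assumed combinations, by 0.02, and in none with a 2-point OS 4 effect. At the planning 40% without steroids, even crude reversal needs 7.5(1 − w) < 4.0, so w > 0.467, which means s above 0.1867/0.72, about 26% of all patients. The documents support neither such a share nor harm in OS 4. Nor must the No estimate disagree with the Population 2 result; it can.

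**Conclusion.** The point holds in a limited form. As written, the steroid No level mixes Population 2 with OS 4 patients, and the treatment-by-steroid term takes up any difference in treatment effect between OS 4 and OS 5/6. Under the stated assumptions the ratio of odds ratios moves from 0.81 to 0.84-1.02 with no OS 4 effect, and to about 0.83-0.92 with a 2-point effect. An apparent interaction of about 1.17 can arise where none exists. This rests on a smaller OS 4 effect and mostly steroid-free OS 4 patients. Both are inferences, and with 20% steroid use in OS 4 the distortion is smaller. No primary or gated decision changes. I class it as a cheap improvement to the interpretability of the steroid estimates.

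**What to change.** In SAP 6.14 and Table KHAA.6.12, specify that for the primary endpoint the steroid Yes/No estimates and interaction test are run within baseline OS 5/6. Show OS 5/6 patients on steroids beside Population 2. Limit the steroid-by-remdesivir groups of Appendix 3 in the same way. Keep the all-ITT split as a descriptive display, and leave OS 4 reported under baseline severity.

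The No level will then contain the same patients as Population 2. Because Table KHAA.6.12 uses LOCF here, its estimate should be read beside the supportive LOCF analysis of Population 2 in Table KHAA.6.5, not the multiple-imputation primary result. Steroid use is not randomized, so the restricted contrast remains observational; the change removes only the OS 4 component.

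The cost is SAP wording and one subset condition in the program, with no new data and no effect on alpha. The downside is that OS 4 patients leave this one interaction test.
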